RESEARCH PROTOCOL

Version 1.5

Date 10/6/2016

Research Title: Objective, Prospective Measurement of Anterior Chamber Cell Grading Using Anterior Chamber Ocular Coherence Tomography

Short Title: Prospective OCT Measurement of AC Cells

Purpose:

- To determine the feasibility of objective measurement of anterior chamber (AC) cell count utilizing
 - the SPECTRALIS (Heidelberg Engineering, Franklin, MA) spectral domain optical coherence tomography (OCT) system
 - the iSCAN (Optovue, Fremont, CA) spectral domain OCT system
- To develop algorithms that automatically differentiate between cells and “noise” in the anterior chamber OCT (AC-OCT) images and objectively measure the cell density
- To correlate the objective AC cell density measurement and the subjective clinical AC cell grading
- To compare the objective AC cell density measurement with subject treatment outcomes

Introduction:

Treatment decisions for patients with uveitis are currently formulated largely on subjective clinical exam data with high interobserver variation.¹ The most used and most accurate of these subjective clinical data is anterior chamber (AC) cell grade, a measure of intraocular inflammation.¹ AC cell grade is measured by experienced clinicians who manually count the number of leukocytes in a 1mm by 1mm beam of light in the AC visible through a slit lamp stereoscope. The result is a “grade” for AC cells on a nonlinear, ordinal scale as follows: grade 0 is <1 cell, grade 0.5+ is 1-5 cells, grade 1+ is 6-15 cells, grade 2+ is 16-25 cells, grade 3+ is 26-50 cells, and grade 4+ is >50 cells.² The wide range of cells included in the higher grades means that a large change in anterior chamber inflammation might go unnoticed. For example, a patient with 28 cells at their last visit (grade 3+) but 48 cells at their current visit (still grade 3+) would have their 71% increase in intraocular inflammation go unnoticed, as they are still grade 3+. This has concerning implications for both the treatment of patients with intraocular inflammation and the evaluation of interventions that target intraocular inflammation (such as pharmaceuticals).

People with uveitis and people who recently underwent cataract extraction surgery often have intraocular inflammation on clinical exam. Those with uveitis are generally given anti-inflammatory medication to resolve their inflammation. Inflammation after cataract extraction surgery is generally self-resolving.

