Optical Coherence Tomography (OCT) uses infrared light with a central wavelength of 840 - 870 nm from a superluminescent diode to scan ocular structures and produce cross sectional and three dimensional images.^{3,4} It is considered a Class 1 laser product that, “does not pose any safety hazard whatsoever.”^{3,5}

RUTGERS APPROVED
THE STATE UNIVERSITY
OF NEW JERSEY

IRB ID: Pro20160000585
Approval Date: 10/24/2016
Expiration Date: 7/19/2017

Title: Prospective OCT Measurement of AC Cells

PI: [name]

OCT machines are used widely in ophthalmology clinics to image the retina and objectively measure glaucoma progression. It can also be used to image the anterior chamber.

A few studies have evaluated the feasibility of imaging the AC to objectively measure intraocular inflammation using optical coherence tomography (OCT). Many of these have used older, time domain OCT (TD-OCT) devices, with resolutions larger than most leukocytes.⁶⁻⁸ One has used newer, spectral domain OCT (SD-OCT) technology with promising results.⁹ No study that we are aware of, however, has either used the SPECTRALIS or iSCAN SD-OCT systems for these measurements, or correlated these measurements against clinical outcomes. We plan to use the SPECTRALIS and iSCAN SD-OCT systems to image the AC of subjects with intraocular inflammation, automate the objective reading of AC cell count from these images, correlate the objective count with the subjective clinical grade, and observe if the correlation is strong enough to guide treatment decisions.

Hypothesis:

Automated, objective measurement of anterior chamber cell count with the SPECTRALIS (Heidelberg Engineering, Franklin, MA) and iSCAN (Optovue, Fremont, CA) spectral domain optical coherence tomography systems cannot be used to guide the treatment of patients with intraocular inflammation.

Methods:

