This is a prospective clinical imaging study. Treatment and follow up of subjects will not be altered through this study. Subjects will be selected from the pool of patients in the Doctors Office Center (DOC) at New Jersey Medical School/University Hospital who attend the Wednesday Uveitis clinic. The clinic is staffed by two staff physicians ([name] and [name]) and a rotating staff of NJMS ophthalmology residents. Non-patient control subjects may also have an opportunity to participate in this study; this group will include friends and relatives of enrolled subjects and any person who volunteers for the study (such as those who saw the study registered on clinicaltrials.gov). Up to 300 subjects will be enrolled.

Three groups of subjects will be enrolled: one “uveitis imaging” group, one “cataract imaging” group, and one “control” group. The uveitis imaging group will include subjects with uveitis. The cataract imaging group will include subjects who have just undergone cataract extraction surgery within the previous 30 days. The third group will function as a control. Inclusion criteria for both imaging groups will include an age over 18 years old and active anterior chamber inflammation in at least one eye as diagnosed by clinical exam. Inclusion criteria for the uveitis imaging group will also include a diagnosis of uveitis. Inclusion criteria for the cataract imaging group will also include having recently undergone cataract extraction surgery within the previous 30 days. Inclusion criteria for controls will include an age of 18 years old in subjects with and without uveitis who do not have active intraocular inflammation based on clinical exam. Exclusion criteria for all three groups will include corneal opacities in the affected eye that would limit objective measurement by OCT and anyone judged unable to understand or consent to study participation. The two staff physicians will identify eligible subjects for inclusion. Controls will be recruited from the same clinic described above. Controls will include patients who meet the inclusion criteria above, and also non-patient control subjects who meet the inclusion criteria above.

RUTGERS APPROVED
2

Title: Prospective OCT Measurement of AC Cells

PI: [name]

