Prior to the scan, non-patient control subjects will also undergo a brief, non-contact ocular exam by either [name] or [name], to ensure that they meet inclusion and do not meet exclusion criteria (e.g. they have no intraocular inflammation and no corneal opacities); this exam will not require any eye drops.

The study will be thoroughly explained to any potential subjects identified by the two staff physicians. Subjects recruited will be patients of the investigators or non-patient control subjects (such as the relatives and friends of those patients who attend the clinic with them). Any potential subject will be asked to participate and will have the study thoroughly explained to them. They will have the opportunity to ask questions and will be given ample time to decide on participation or nonparticipation. They will also have the opportunity to discuss the study and their participation with relatives or friends. They will be notified that their participation is completely optional and that participation or nonparticipation in this study will not alter or affect their relationship with their doctor or any of their healthcare providers. To avoid coercion, the study risks will be carefully explained to subjects and it will be emphasized that participation is completely optional and not required for their medical care or for their relationship with their physician. A subject's participation or nonparticipation in this study will not alter or affect their medical care in any way. Treatment of subject's uveitis will still be based on clinical examination, and not on any information obtained from the OCT imaging. The consent process will be administered by any of the following study staff ("study personnel obtaining consent"): [name], study coordinator and NJMS medical student; [name] and uveitis specialist; and [name] and uveitis specialist.

The study personnel obtaining consent will ensure each subject has verbal fluency of the English language and is well able to understand the study procedures and consent form. People of all economic classes and educational levels will be invited equally to participate in the study. Minority status will also not be a factor in participation. Children, prisoners, and pregnant woman will not be included in this study. Pregnant woman will not be included due to the majority of expected eligible patients being non-pregnant.

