Subject risks include potential breach of confidentiality of information collected and the loss of 10-20 minutes of time required to complete the OCT scan process. The risk of breach of confidentiality of information is minimal due to the lack of collection of sensitive information and will be further minimized by storing data in locked and password protected files, as described above. Subject benefits include potentially increased understanding of intraocular inflammation and the new management standards that may be applied to their, and others', uveitis treatment in the future.

All subject data obtained will be confidential. Data will only be released in aggregate and no subjects' personal identifiers will be revealed.

De-identified image data from the SPECTRALIS and iSCAN OCT systems will be analyzed two ways. The first analysis methodology will be the manual identification of leukocytes on the OCT image by the staff uveitis specialists. The second analysis methodology will be the automatic identification of leukocytes on the OCT image by computer algorithm. The AC cell count results of the two analysis methodologies will be compared to subject's clinical AC cell grading. Statistical analysis using T-test and other statistical tools will be used to compare the study and the clinical AC cell count methodologies. Study AC cell count results will also be correlated with the actual subject treatment plans and outcomes to test the null hypothesis that the study results would not have been able to correctly guide subject treatment decisions.

References:

Title: Prospective OCT Measurement of AC Cells

PI: [name]

3. *User Manual: SPECTRALIS HRA+OCT.* Heidelberg Engineering GmbH;2012.
4. ISCAN. *Optovue* 2016; <http://www.optovue.com/products/iscan/>, 2016.
5. Laser Safety Information. *Laser Institute of America* 2016; https://www.lia.org/subscriptions/safety_bulletin/laser_safety_information. Accessed March 31, 2016.

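### Treatment plans are set by the clinical exam, so correlating OCT counts with them shows agreement with the exam and cannot by itself show that OCT would have guided treatment correctly

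*Combined protocol and SAP*

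**What the plan says.** The Hypothesis section states the null: automated OCT measurement "cannot be used to guide the treatment of patients with intraocular inflammation". The final Methods paragraph says how it will be tested. OCT cell counts will be correlated with both the treatment plans and the outcomes of the subjects, "to test the null hypothesis that the study results would not have been able to correctly guide subject treatment decisions". No coefficient, model, adjustment, significance level or definition of outcome is given for this step.

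The consent part of Methods says that treatment of uveitis "will still be based on clinical examination, and not on any information obtained from the OCT imaging". The opening of Methods adds, for all subjects, that the study changes neither treatment nor follow-up.

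Outcomes also appear as an aim of their own under Purpose: "To compare the objective AC cell density measurement with subject treatment outcomes". Methods plans repeat scans at scheduled follow-up visits, so that both inflammation and its resolution can be seen. The list of items taken from the medical record names inflammation status and ocular history, but not treatment.

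**The concern.** The null is about correctness, and the plan is the wrong yardstick for that. Each plan comes from the exam, so a correlation between OCT and plan asks only whether OCT goes along with what the exam led the clinician to do. This works against the study's own rationale in two ways.

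- **OCT can succeed without adding anything.** If OCT tracks the exam grade and the grade drives the plan, OCT will correlate with the plan even when it holds no further information.
- **OCT gets no credit where it should be most useful.** The Introduction gives a rise from 28 to 48 cells that stays within grade 3+ and passes unnoticed. A plan based on the grade need not move, so an OCT count that detects the rise gains nothing in this comparison.

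At stake is the published conclusion. A significant plan correlation could be reported as showing that OCT can correctly guide treatment, when it shows that OCT agrees with the exam.

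**Working it through.** The protocol states no correlation target, alpha, power or group sizes for this analysis, so there is no figure to reproduce. The check has four parts.

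**1. The passages side by side.** The final Methods paragraph takes the actual plan as one of two references for a correct decision. The consent part of Methods says where that plan comes from: the exam, without OCT. Nothing in the protocol supplies an independent criterion for a correct plan. The plan correlation is therefore a measure of agreement.

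**2. How far a count can move within a grade.** Input: the grading scale in the Introduction (grade 0.5+ is 1 to 5 cells; "grade 1+ is 6-15 cells, grade 2+ is 16-25 cells, grade 3+ is 26-50 cells"). Formula: upper limit / lower limit − 1.
- 0.5+: 5/1 − 1 = 400%
- 1+: 15/6 − 1 = 150%
- 2+: 25/16 − 1 = 56%
- 3+: 50/26 − 1 = 92%
- The protocol's own example: 48/28 − 1 = 71%

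A plan that follows the grade need not respond to any of these changes.

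**3. Correlation through the exam alone.** Assumptions, none of them in the protocol: two-sided alpha 0.05, one independent observation per subject, normal variables, and OCT independent of plan given grade.
- OCT-plan correlation: r(OCT, plan) = r(OCT, grade) × r(grade, plan) = 0.5 × 0.7 = 0.35.
- Partial correlation given grade: (0.35 − 0.5 × 0.7) / √[(1 − 0.25)(1 − 0.49)] = 0.
- Chance that the unadjusted test is significant: Φ(atanh(r) × √(n − 3) − 1.96).
 - n=100: Φ(0.3654 × 9.849 − 1.96) = Φ(1.64) = 0.95
 - n=50: Φ(0.3654 × 6.856 − 1.96) = Φ(0.545) = 0.71
- Simulation of 4,000 studies at n=100: unadjusted rejection 0.954, grade-adjusted rejection 0.053.
- Range: with both component correlations varied from 0.3 to 0.9, the OCT-plan correlation runs from 0.09 to 0.81. Unadjusted rejection at n=100 runs from 0.14 to about 1.00. The partial correlation is 0 throughout.

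The direction follows from the protocol's statement of how treatment is set. The size depends on the assumed correlations.

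**4. What a grade- and treatment-adjusted analysis could detect.** As a rough guide only, treat it as a partial correlation with two adjusting variables and one visit pair per subject. The value detectable with 80% power is tanh[(1.960 + 0.842) / √(n − 5)].
- n=100: tanh(0.287) = 0.28
- n=50: tanh(0.418) = 0.39

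A categorical grade and a yes/no outcome would change these values, and so would further visits per subject. They show that power is uncertain, not that the analysis is out of reach.

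**The case against.** **The test uses outcomes as well as plans.** This stands. A reader might infer that the whole test is circular, and the protocol does not support that. Outcomes are a stated purpose, follow-up scans are planned, and a later outcome could in principle show whether a plan worked. But the protocol does not say how plans and outcomes combine into a judgement of correctness, and outcome is not defined. Outcomes also follow exam-based treatment, and the Introduction says that inflammation after cataract surgery generally resolves by itself. An unadjusted correlation of OCT with outcome therefore leaves open whether OCT adds to the exam or only tracks it.

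**The Hypothesis section does not require OCT to improve on the exam.** This also stands. Agreement with exam-based decisions is legitimate feasibility evidence, and adjustment for grade is not needed to show it. It is needed only for a claim beyond agreement, so the adjusted analysis belongs in a secondary place.

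**The protocol has a strength criterion.** The Introduction plans to "observe if the correlation is strong enough to guide treatment decisions". A reader might take this as an unquantified threshold for the plan correlation. In context it refers to the correlation of OCT with clinical grade. No value is given for either correlation, but that is missing detail and would not carry the point alone.

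**Numbers.** "Up to 300 subjects will be enrolled" is a ceiling over three groups, and the controls have no active inflammation. It should not be used as the sample size of a plan correlation, which is why the working stops at n=100.

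**The exam is more than the grade.** The protocol says that treatment rests on clinical examination, not on the cell grade alone. The calculation through the grade is therefore a simplification, but the plan remains a product of the exam either way.

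**Conclusion.** The point holds for the plan half of the test. Because plans come from the exam and not from OCT, correlation with plans shows agreement and cannot alone reject a null about correct guidance. Under the assumed correlations of 0.5 and 0.7, an OCT count with no information beyond the grade would give a significant plan correlation in about 95% of studies at n=100. This is an illustration and not an estimate for this trial. The outcome half is not circular in this way; its weakness is the lack of adjustment if it is used to claim more than agreement.

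A reader might also infer a risk to patients, and the documents do not support that, since care is unchanged by the study. The consequence is confined to what can be concluded. It is worth correcting before analysis because the remedy is specific and cheap.

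**What to change.** 1. **Relabel the plan analysis.** In the final Methods paragraph, describe OCT versus treatment plan as agreement with exam-based decisions and report it with a confidence interval. Limit its conclusion to *OCT agrees with exam-based decisions*. State that it will not be used alone to reject the null about correct guidance.
2. **Base any wider statement on outcomes.** Using the follow-up visits already planned, model next-visit inflammation status, defined in advance, on current grade and treatment given, then add the current automated OCT count. Allow for repeated visits and for eyes within a subject. Present this as secondary, with a confidence interval. State that the endpoint is itself exam-based. Because the current grade is measured with error, a repeat exam could also add information, so a positive result would not show OCT to be better than the exam. A non-significant result should not be read as proof of no added value.
3. **Extract the treatment data.** The final Methods paragraph already needs them. The list of record items may not be exhaustive, but treatment should be named in it.

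**Cost:** a reworded paragraph, one extraction item and one further model, with no extra visits and no change in care. The downsides are a narrower conclusion from the plan analysis, some added extraction and analysis work, and uncertain power for the secondary analysis.
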